9.2. PATIENT WITHDRAWAL

A patient is derived as having prematurely discontinued the study if investigator "Yes/No" answer to question "Has the patient prematurely discontinued the study?" on the "Early study discontinuation" eCRF form is "Yes", and the reason for premature discontinuation is that as reported by the investigator.

Number and percentage of patients who prematurely discontinued the study will be summarized on the ITT population, on the Treated population, and on the PP population, overall and by reason for premature discontinuation. Results will be provided on the pooled data across the two arms and by arm.

9.3. FLOW CHART

To summarize this information, a flow chart will be produced. It will take the following form:

10. DEMOGRAPHIC AND OTHER BASELINE CHARACTERISTICS

Analyses will be carried out on the ITT population, in a descriptive manner, using appropriate statistics as described in Section 6.1. Results will be provided on the pooled data across the two arms and by arm.

If the ITT population and the PP population differ by more than 10% (that is, if more than 10% of patients in the ITT population are finally excluded from the PP population), the analyses will be further carried out on the PP population.

These results will also be presented in the appendix for patients of the optional sub-study who had a biopsy at V1 and for patients of the optional sub-study who had a biopsy at V9. These results will be provided based on the pooled data across the two arms and by arm.

Number and percentage of patients with and without each eligibility criterion will be provided on the pooled data across the two arms and by arm.

10.1. DEMOGRAPHIC CHARACTERISTICS

- Gender (qualitative parameter: "Male", "Female")
- Age in years (quantitative parameter) calculated at patient's inclusion as follows:

Date of randomization - Date of birth rounded to the nearest lower integer.

- Phototype (qualitative parameter: "1", "2", "3", "4", "5", "6")
- Profession (qualitative parameter: "Nursing staff", "Cleaning, maintenance housekeeping, personal assistance", "Hairdresser"; "Beautician", "Retired", "Public works", "Other")
- Working test (qualitative parameter: "Positive", "Negative", "Doubtful", "Not applicable")
- Aggravating factors of occupational (qualitative parameter: "Yes", "No")
 - o If "Yes", of an irritant nature? (qualitative parameter: "Yes", "No")
 - Please describe (qualitative parameter in plain terms)
 - o If "Yes", of an allergic nature? (qualitative parameter: "Yes", "No")
 - Please describe (qualitative parameter in plain terms)
 - Contact allergy confirmed by allergological tests? (qualitative parameter: "Yes", "No")
- Aggravating factors at home and/or leisure activities (qualitative parameter: "Yes", "No")
 - o If "Yes", of an irritant nature? (qualitative parameter: "Yes", "No")
 - Please describe (qualitative parameter in plain terms)
 - o If "Yes", of an allergic nature? (qualitative parameter: "Yes", "No")
 - Please describe (qualitative parameter in plain terms)

10.2. HISTORY OF THE DISEASE

- Time since diagnosis of CHE (quantitative parameter) calculated at patient's inclusion as follows:

 Date of inclusion Date of diagnosis of CHE
 365.25 rounded to one decimal place.
- Previous treatments for CHE:
 - o Ciclosporin (qualitative parameter: "Yes", "No")
 - If "Yes", duration in months (quantitative parameter)
 - o Methotrexate (qualitative parameter: "Yes", "No")
 - If "Yes", duration in months (quantitative parameter)
 - o Alitretinoine (qualitative parameter: "Yes", "No")
 - If "Yes", duration in months (quantitative parameter)
 - o Oral corticosteroid (qualitative parameter: "Yes", "No")

- If "Yes", duration in months (quantitative parameter)
- o Phototherapy (qualitative parameter: "Yes", "No")
 - If "Yes", type (qualitative parameter in plain terms)
 - If "Yes", number of sessions (quantitative parameter)
- o Powerful or very powerful dermocorticoids (qualitative parameter: "Yes", "No")
- o Topical tacrolimus (qualitative parameter: "Yes", "No")
- Time off work in connection with CHE? (qualitative parameter: "Yes", "No")
- Therapeutic education session for CHE already completed? (qualitative parameter: "Yes", "No")
- History of atopy
 - o History of personal atopy (qualitative parameter: "Yes", "No")
 - o Atopic dermatitis (qualitative parameter: "Yes", "No")
 - o Allergic rhinitis (qualitative parameter: "Yes", "No")
 - If "Yes", (qualitative parameter: "Intermittent", "Mild persistent", "Severe persistent")
 - o Asthma (qualitative parameter: "Yes", "No")
 - If "Yes", (qualitative parameter: "Intermittent", "Mild persistent", "Moderate persistent", "Severe persistent")
 - o Allergic conjunctivitis (qualitative parameter: "Yes", "No")
 - o Family history of atopy (qualitative parameter: "Yes", "No")
 - o Currently off work due to CHE? (qualitative parameter: "Yes", "No")
 - If yes, duration in months (quantitative parameter)

10.3. BIOLOGICAL CHECK-UP

- Hemoglobin in g/dL (quantitative parameter)
- Platelets in G/L (quantitative parameter)
- Leukocytes in G/L (quantitative parameter)
- Eosinophilic polymorphs in G/L (quantitative parameter)
- Hepatitis B serology (qualitative parameter: "Positive", "Negative", "Hepatitis B cured", "Vaccination status")
- Hepatitis C serology (qualitative parameter: "Positive", "Negative")
- HIV serology (qualitative parameter: "Positive", "Negative")
- Total IgE
 - o Sample taken (qualitative parameter: "Yes", "No")
 - If "No", why? (qualitative parameter in plain terms)
 - o Result in kUI/L (quantitative parameter)

10.4. ALLERGY ASSESSMENT

- Known sensitization to pneumallergens (qualitative parameter: "Yes", "No")
 - o If "Yes, the answer "Yes" or "No" (qualitative parameter) is expected for the following pneumallergens: DP/DF mites, Cockroach (native), Cat, Dog, Grass, Plantain, Parietaria, Mugwort, Ragweed, Alternaria, Aspergillus, Latex(native), Birch, Olive, Plane tree, Cypress, Type of allergen(s) unknown to the patient
- Food allergies (qualitative parameter: "Yes", "No")
 - o If "Yes, the answer "Yes" or "No" (qualitative parameters) is expected for anaphylaxis, oral syndrome and eviction regarding various food. The answer "No", "Partial" or "Complete" is expected for tolerance. The food concerned are: Egg white, Fish, Shrimp, Cow's milk, Celery, Apple, Peach, Peanut, Kiwifruit, Hazelnut, Nuts, Sesame, Wheat, Soya, Cashew nuts, Other.
- Other allergies: Contact allergy suspected on examination? (qualitative parameter: "Yes", "No")
- Allergological tests carried out? (qualitative parameter: "Yes", "No")
 - o If "Yes", the following positive patch tests will be ticked off (qualitative parameters): None,

Potassium dichromate, P-Phenylenediamine, Thiuram-mix, Neomycin Cobalt chloride, Benzocaine, Nickel sulphate, Clioquinol, Colophonium, Paraben Mix (Butyl, ethyl, methyl, proppyl Paraben), N'Isopropylphenylenediamine, LANOLIN, Mercapto Mix, Epoxy resin, Bisphenol A, Peru Balsam (MYROXYLON PERERAE), 4-tert-Butylphenoformaldehyde resin, Mercaptobenzothiazole, FORMALDEHYDE, Fragrance mix 1, Sesquiterpene Lactone Mix, Quaternium 15, 2-Methoxy-6-n-pentyl-4-benzoquinone (Primine), Methylchloroisothiazolinone Methyl Isothiazolinone, Budesonide, Tixocortol-21-Pivalate, Methyldibromo Glutaronitrile, Fragrance mix 2, Hydroxymethylpentylcyclohenecarboxaldehyde, Methyl Isothiazolinone at 2000 ppm WATER, Textile Dye mix, Hydrocortisone-17-Butyrate, 3-(Dimethylamino)-1-Propylamine (DMAPA), Amerchol, Benzalkonium Chloride 0. 1% water, Limonene Hydroperoxide, Laurylglucoside, Benzyl Alcohol (Benzyl Alcohol), Linalool Iodopropynyl Butylcarbamate, 2-n-Octyl-4 Isothiazolin-3-one Hydroperoxide, (octylisothiazolinone), Decylglucoside, Other.

• If "Other", specify (qualitative parameter in plain terms)

10.5. CLINICAL EXAMINATION

10.5.1. Clinical examination

- Weight in kg (quantitative parameter)
- Height in cm (quantitative parameter)
- SBP (systolic blood pressure) in mmHg (quantitative parameter)
- DBP (diastolic blood pressure) in mmHg (quantitative parameter)
- Pulse in bpm (quantitative parameter)
- Temperature in °C (quantitative parameter)

10.5.2. Ocular symptoms

- Ocular symptoms (qualitative parameter: "Yes", "No")
- If "Yes".
 - o Tearing (qualitative parameter: "Yes", "No")
 - o Tingling, foreign body sensation (qualitative parameter: "Yes", "No")
 - o Pruritus (qualitative parameter: "Yes", "No")
 - o Dry syndrome (qualitative parameter: "Yes", "No")
 - o Eye burns (qualitative parameter: "Yes", "No")
 - o Does the patient have a red eye on clinical examination? (qualitative parameter: "Yes", "No")
 - o Eye involved (qualitative parameter: "Right", "Left", "Both eyes")
 - Has the patient had an initial ophthalmological examination? (qualitative parameter: "Yes", "No")

11. DISEASE ASSESSMENT

Analyses will be carried out on the ITT population, in a descriptive manner, using appropriate statistics as described in Section 6.1. Results will be provided on the pooled data across the two arms and by arm.

If the ITT population and the PP population differ by more than 10% (that is, if more than 10% of patients in the ITT population are finally excluded from the PP population), the analyses will be further carried out on the PP population.

These results will also be presented at baseline and at visit 9 in the appendix for patients of the optional substudy who had a biopsy at V1 and for patients of the optional sub-study who had a biopsy at V9. These results will be provided based on the pooled data across the two arms and by arm.

11.1. HAND ECZEMA (AT BASELINE)

- Involvement (qualitative parameter: "Unilateral", "Bilateral)
- Involvement (qualitative parameter: "Palmar only", "Dorsal only", "Palmar and dorsal)
- Involvement n°1 (qualitative parameter: "Vesicles", "Cracks", "Hyperkeratosis", "Pulpitis")
- Involvement n°2 (qualitative parameter: "Vesicles", "Cracks", "Hyperkeratosis", "Pulpitis")
- Involvement n°3 (qualitative parameter: "Vesicles", "Cracks", "Hyperkeratosis", "Pulpitis")
- Involvement n°4 (qualitative parameter: "Vesicles", "Cracks", "Hyperkeratosis", "Pulpitis")
- Associated nail disease (qualitative parameter: "Yes", "No")

11.2. REMOTE ECZEMA OF THE HANDS (AT BASELINE)

- Eczema away from the hands (qualitative parameter: "Yes", "No")
 - o If "Yes", Feet (qualitative parameter: "Yes", "No")
 - o If "Yes", Head and neck (qualitative parameter: "Yes", "No")
 - o If "Yes", Trunk and/or limbs (excluding folds) (qualitative parameter: "Yes", "No")
 - o If "Yes", Folds (qualitative parameter: "Yes", "No")

11.3. MODIFIED TOTAL LESION SYMPTOM SCORE (AT BASELINE, V3, V5, V7 AND V9)

- mTLSS achieved (qualitative parameter: "Yes", "No")
 - o If "No", why? (qualitative parameter in plain terms)
- mTLSS score (quantitative parameter: from 0 (no symptoms) to 21 (multiple severe symptoms). The result is obtained by adding the score for each of the following items:

Parameter	Description of severity*		
Erythema	0 = Absent 1 = Faint erythema		
	2 = Prominent redness		
	3 = Deep intense red color		
Scaling	0 = Absent1 = Slight flaking over limited areas, mostly fine scales		
	2 = Flaking over widespread area(s), coarser scales		
	3 = Desquamation covering over 30% of the hand, with coarse thick scales		

visible erosion or excoriation	Lichenification/hyperkeratosis	0 = Absent 1 = Mild thickening with exaggerated skin lines over limited areas 2 = Palpable thickening over widespread area(s) 3 = Prominent thickening over widespread area(s) with exaggeration of normal skin markings
1 = Dermal swelling over less than 10% of hands 2 = Definite dermal swelling over more than 10% of hand 3 = Dermal swelling with skin induration over widespread area(s) Fissures 0 = Absent 1 = Cracked skin affecting a small area of the hand 2 = Cracked skin affecting multiple areas of the hand and causing pain 3 = One or more deep fissures and causing bleeding or severe pain Pruritus/pain 0 = Absent 1 = Occasional, slight discomfort a few times per day 2 = Intermittent, causing discomfort frequently during the day	Vesiculation	1 = Scattered vesicles affecting up to 10% of hand, without erosion 2 = Scattered or clustered vesicles affecting up to 30% of hand, without visible erosion or excoriation 3 = High density of vesicles extending over large area(s), or with erosion
1 = Cracked skin affecting a small area of the hand 2 = Cracked skin affecting multiple areas of the hand and causing pain 3 = One or more deep fissures and causing bleeding or severe pain Pruritus/pain 0 = Absent 1 = Occasional, slight discomfort a few times per day 2 = Intermittent, causing discomfort frequently during the day	Oedema	1 = Dermal swelling over less than 10% of hands 2 = Definite dermal swelling over more than 10% of hand
1 = Occasional, slight discomfort a few times per day 2 = Intermittent, causing discomfort frequently during the day	Fissures	1 = Cracked skin affecting a small area of the hand 2 = Cracked skin affecting multiple areas of the hand and causing pain
*1 = mild; 2 = moderate; 3 = severe		1 = Occasional, slight discomfort a few times per day 2 = Intermittent, causing discomfort frequently during the day 3 = Persistent or interfering with sleep

11.4. INVESTIGATOR GLOBAL ASSESSMENT (AT BASELINE, V3, V5, V7 AND V9)

- IGA achieved (qualitative parameter: "Yes", "No")
 - o If "No", why? (qualitative parameter in plain terms)
- IGA score (quantitative parameter: from 0 ("Clear") to 4 ("Severe"))

Score	Morphological Description
0 – Clear	No inflammatory signs of atopic dermatitis (no erythema, no induration/papulation, no lichenification, no oozing/crusting). Post-inflammatory hyperpigmentation and/or hypopigmentation may be present.
1 – Almost clear	Barely perceptible erythema, barely perceptible induration/papulation, and/or minimal lichenification. No oozing or crusting.
2 – Mild	Slight but definite erythema (pink), slight but definite induration/papulation, and/or slight but definite lichenification. No oozing or crusting.
3 – Moderate	Clearly perceptible erythema (dull red), clearly perceptible induration/papulation, and/or clearly perceptible lichenification. Oozing and crusting may be present.
4 – Severe	Marked erythema (deep or bright red), marked induration/papulation, and/or marked lichenification. Disease is widespread in extent. Oozing or crusting may be present.

• IGA binary score (qualitative parameter: "Clearance or almost clearance", "From mild to severe")

11.5. ECZEMA AREA AND SEVERITY INDEX (AT BASELINE, V3, V5, V7 AND V9)

- EASI achieved (qualitative parameter: "Yes", "No")
 - o If "No", why? (qualitative parameter in plain terms)
- EASI score (quantitative parameter: from 0 (no symptoms) to 72 (multiple severe symptoms)). The result is obtained with this scoring table:

Body region		Erythema	Edema/	Excoriation	Lichenification	Region score	Multiplier	Score per boy	
			Papulation					region	
Head/neck	(+	+	+)	×	× 0.1		
Trunk	(+	+	+)	×	× 0.3		
Upper extremities	(+	+	+)	×	× 0.2		
Lower extremities	(+	+	+)	X	× 0.4		
		The final EASI score is the sum of the 4 region scores:							

- The severity of each sign (Erythema, Edema/Papulation, Excoriation and Lichenification) is assessed on a scale of 0 to 3 (qualitative parameter: 0="None", 1="Mild", 2="Moderate", 3="Severe")
- The area of involvement of each body region is assessed on a scale of 0 to 6 (qualitative parameter) based on the following table:

% involvement	0	1 - 9%	10 - 29%	30 - 49%	50 - 69%	70 - 89%	90 - 100%
Region score	0	1	2	3	4	5	6

11.6. DERMATOLOGY LIFE QUALITY INDEX (AT BASELINE, V3, V5, V7 AND V9)

- DLQI achieved (qualitative parameter: "Yes", "No")
 - o If "No", why? (qualitative parameter in plain terms)
- DLQI score (quantitative parameter: from 0 ("Meaning no impact of skin disease on quality of life") to 30 ("Meaning maximum impact on quality of life")). The result is obtained by adding the score for each of the following items:

Item	Quotation
1 - Over the last week, how itchy, sore, painful or stinging has your skin been?	3 = Very much 2 = A lot 1 = A little 0 = Not at all
2 - Over the last week, how embarrassed or self conscious have you been because of your skin?	3 = Very much 2 = A lot 1 = A little 0 = Not at all
3 - Over the last week, how much has your skin interfered with you going shopping or looking after your home or garden?	3 = Very much 2 = A lot 1 = A little 0 = Not at all or Not relevant
4 - Over the last week, how much has your skin influenced the clothes you wear?	3 = Very much 2 = A lot 1 = A little 0 = Not at all or Not relevant
5 - Over the last week, how much has your skin affected any social or leisure activities?	3 = Very much 2 = A lot 1 = A little 0 = Not at all or Not relevant

6 - Over the last week, how much has your skin made it difficult for you to do any sport?	3 = Very much 2 = A lot 1 = A little 0 = Not at all or Not relevant
 7A - Over the last week, has your skin prevented you from working or studying? 7B - If "No", over the last week how much has your skin been a problem at work or studying? 	3 = Yes If No, see next 7B 2 = A lot 1 = A little 0 = Not at all
8 - Over the last week, how much has your skin created problems with your partner or any of your close friends or relatives?	3 = Very much 2 = A lot 1 = A little 0 = Not at all or Not relevant
9 - Over the last week, how much has your skin caused any sexual difficulties?	3 = Very much 2 = A lot 1 = A little 0 = Not at all or Not relevant
10 - Over the last week, how much of a problem has the treatment for your skin been, for example by making your home messy, or by taking up time?	3 = Very much 2 = A lot 1 = A little 0 = Not at all or Not relevant

• DLQI binary score (qualitative parameter: "0 or 1", "Greater than 1")

11.7. 5-LEVEL EQ-5D (AT BASELINE, V3, V5, V7 AND V9)

- EQ-5D-5L achieved (qualitative parameter: "Yes", "No")
 - o If "No", why? (qualitative parameter in plain terms)
- EQ-5D-5L: 5 domains (qualitative parameter: from "Level 1" to "Level 5") (2)
 - Presented as 12345 (qualitative parameter: from "Level 1" to "Level 5" for each domain) where 1 represents the score in the first domain (MO: mobility), 2 the score in the second domain (SC: self-care), 3 the score in the third domain (UA: usual activities), 4 the score in the fourth domain (PD: pain/discomfort) and 5 the score in the fifth domain (AD: anxiety/depression).

Item	Quotation
Mobility	1 = I have no problems in walking about
	2 = I have slight problems in walking about
	3 = I have moderate problems in walking about
	4 = I have severe problems in walking about
	5 = I am unable to walk about
Self-care	1 = I have no problems washing or dressing myself
	2 = I have slight problems washing or dressing myself
	3 = I have moderate problems washing or dressing myself
	4 = I have severe problems washing or dressing myself
	5 = I am unable to wash or dress myself
Usual activities	1 = I have no problems doing my usual activities
	2 = I have slight problems doing my usual activities
	3 = I have moderate problems doing my usual activities
	4 = I have severe problems doing my usual activities
	5 = I am unable to do my usual activities
	-

Pain / discomfort	 1 = I have no pain or discomfort 2 = I have slight pain or discomfort 3 = I have moderate pain or discomfort 4 = I have severe pain or discomfort 5 = I have extreme pain or discomfort
Anxiety / depression	 1 = I am not anxious or depressed 2 = I am slightly anxious or depressed 3 = I am moderately anxious or depressed 4 = I am severely anxious or depressed 5 = I am extremely anxious or depressed

• EQ Visual Analogue Scale (VAS): overall health on a scale from 0 to 100 (quantitative parameter)

11.8. WORK PRODUCTIVITY AND ACTIVITY IMPAIRMENT QUESTIONNAIRE (AT BASELINE AND V9)

- WPAI achieved (qualitative parameter: "Yes", "No")
 - o If "No", why? (qualitative parameter in plain terms)
- WPAI outcomes in impairment percentages (quantitative parameter), with higher numbers indicating
 greater impairment and less productivity, i.e., worse outcomes. The outcomes are calculated from these
 data:

Questions	Modality
Q1 - Are you currently employed (working for pay)?	"No" (skip to question 6) "Yes"
Q2 - During the past seven days, how many hours did you miss from work because of your health problems?	Quantitative parameter
Q3 - During the past seven days, how many hours did you miss from work because of any other reason, such as vacation, holidays, time off to participate in this study?	Quantitative parameter
Q4 - During the past seven days, how many hours did you actually work?	Quantitative parameter (if 0, skip to question 6)
Q5 - During the past seven days, how much did health problems affect your productivity while you were working?	Quantitative parameter (from 0 to 10)
Q6 - During the past seven days, how much did health problems affect your ability to do your regular daily activities, other than work at a job?	Quantitative parameter (from 0 to 10)

- O Work time missed in percent (quantitative parameter) calculated as follows: $\frac{Q^2}{Q^2 + Q^4} * 100$
- Impairment while working due to health in percent (quantitative parameter) calculated as follows:
 Q5 * 10
- Overall work impairment due to health in percent (quantitative parameter) calculated as follows: $\frac{Q^2}{Q^2 + Q^4} + \left[\left(1 \frac{Q^2}{Q^2 + Q^4} \right) * \frac{Q^5}{10} \right] * 100$
- Activity impairment due to health in percent (quantitative parameter) calculated as follows: Q6 *
 10

11.9. PATIENT'S GLOBAL ASSESSMENT OF DISEASE SEVERITY (AT BASELINE, V3, V5, V7 AND V9)

- PaGa achieved (qualitative parameter: "Yes", "No")
 - o If "No", why? (qualitative parameter in plain terms)
- PaGa evaluation (qualitative parameter: "Clear", "Almost clear", "Mild", "Moderate", "Severe")
- PaGa binary evaluation (qualitative parameter: "Clearance or almost clearance", "From mild to severe")

11.10. VISUAL ANALOG SCALES OF PRURITUS, PAIN AND SLEEP LOSS (AT BASELINE, V3, V5, V7 AND V9)

- VAS for measuring pruritus achieved (qualitative parameter: "Yes", "No")
 - o If "No", why? (qualitative parameter in plain terms)
 - VAS for measuring pruritus in mm (quantitative parameter)
- VAS for measuring pain achieved (qualitative parameter: "Yes", "No")
 - o If "No", why? (qualitative parameter in plain terms)
 - VAS for measuring pain in mm (quantitative parameter)
- VAS for measuring sleep loss achieved (qualitative parameter: "Yes", "No")
 - o If "No", why? (qualitative parameter in plain terms)
 - VAS for measuring sleep loss in mm (quantitative parameter)

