6.3.6. Handling of missing value for secondary judgement criteria

For secondary endpoints, all secondary judgement criteria requiring a difference calculation except WPAI (EASI, DLQI, EQVAS of EQ-5D-5L, the several VAS for measuring pruritus, pain or sleep loss, and the laboratory parameters) will be treated as follows:

- If they are completely missing or if more than 25% of items are missing for scores calculated from different assessments (EASI and DLQI) during the first visit, no imputation will be made and the participants will not be considered in any of the analyses.
- For scores calculated from different assessments (EASI and DLQI), if less than 25% of items are missing at the inclusion visit, this will be imputed by the value representing the patient's optimal state.
- If they are completely missing or if more than 25% of items are missing for scores calculated from different assessments (EASI and DLQI) at all visits except the first, no imputation will be made and the participant will not be included in any of the analyses.
- If they are completely missing or if more than 25% of items are missing for scores calculated from different assessments (EASI and DLQI) at the visit 9 for less than 10% of randomized patients, no imputation will be performed.
- If they are completely missing or if more than 25% of items are missing for scores calculated from different assessments (EASI and DLQI) at the visit 9 for more than 10% of randomized patients, but this score is entered for at least one visit between visit 2 and visit 8, the last available data will be used for the analysis of the secondary endpoint.
- For scores calculated from different assessments (EASI and DLQI), if less than 25% of items are missing and this item has been completed for a visit other than the inclusion visit, only the missing item will be imputed using the last available data to complete the score.

The secondary endpoint WPAI will be treated as follows:

• If it is completely missing or if more than 25% of items are missing during the first visit or the visit 9, no

imputation will be made and the participants will not be considered in any of the analyses.

- If less than 25% of items are missing and the missing items are item 1, 2, 3, 5 and/or 6, they will be imputed by the value representing the patient's optimal state.

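### The overall work impairment formula in SAP 11.8 scales only one of its two terms to percent, and SAP 6.3.6 makes no exception for WPAI items skipped by design

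*SAP*

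**What the plan says.** Section 11.8 derives four WPAI outcomes, all in percent, with higher values meaning "greater impairment and less productivity, i.e., worse outcomes". Three are plainly scaled: work time missed is Q2/(Q2+Q4) times 100, impairment while working is Q5 times 10, and activity impairment is Q6 times 10.

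The fourth is headed "Overall work impairment due to health in percent (quantitative parameter) calculated as follows". In the text extracted from the PDF its formula runs "Q^2}{Q^2 + Q^4} + \left[\left(1 \frac{Q^2}{Q^2 + Q^4} \right) * \frac{Q^5}{10} \right] * 100". The superscripts are item numbers and a minus sign after the 1 has been lost; neither matters here. What matters is that the square bracket opens after the first term and closes before the multiplication by 100.

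The question table in 11.8 prints two skips. A patient who is not employed is told to "skip to question 6", and the entry for hours actually worked reads "Quantitative parameter (if 0, skip to question 6".

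Section 6.3.6 drops a participant from the WPAI analyses, without imputation, when the questionnaire is wholly missing or "more than 25% of items are missing during the first visit or the visit 9". Below that threshold, when "the missing items are item 1, 2, 3, 5 and/or 6, they will be imputed by the value representing the patient's optimal state". Item 4 has its own rule, based on a 35-hour week. Nothing is said about items left blank because the form told the patient to skip them.

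Section 13.2.5 analyses the visit 9 minus visit 1 change in each of the four outcomes separately, by ANCOVA.

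**The concern.** Work productivity is a named secondary objective (section 4) and endpoint (section 5.2.2). An outcome declared in percent adds a fraction to a percentage, although the same section multiplies that same fraction by 100 for work time missed. Absenteeism then carries almost no weight. The ordering can invert: someone unable to work all week scores 1%, while someone present all week with Q5 = 5 scores 50%.

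The missing-item rule adds a second problem in patients the SAP itself expects. Section 10.1 lists retired as a profession, and section 10.2 records whether the patient is currently off work because of hand eczema. These are the patients who meet the skips.

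**Working it through.** The SAP states no numerical WPAI result, so there is no figure to reproduce. The check evaluates the printed rules.

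**Formula.** Inputs from 11.8: a = Q2/(Q2+Q4), where Q2 is hours missed for health, Q4 hours worked, and Q5 a 0 to 10 rating.

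- As printed: P = a + 100 × (1 − a) × Q5/10
- Both terms scaled: F = 100 × [a + (1 − a) × Q5/10]
- Difference: F − P = 100a − a = 99a

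Illustrations on a 35-hour week (the figure in 6.3.6; the patients are hypothetical):

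| Q2 | Q4 | Q5 | a | P | F | F − P |
|---|---|---|---|---|---|---|
| 0 | 35 | 5 | 0 | 50.0 | 50.0 | 0 |
| 7 | 28 | 5 | 0.200 | 40.2 | 60.0 | 19.8 |
| 10 | 25 | 5 | 0.286 | 36.0 | 64.3 | 28.3 |
| 17.5 | 17.5 | 5 | 0.500 | 25.5 | 75.0 | 49.5 |
| 35 | 0 | zero weight | 1 | 1.0 | 100.0 | 99.0 |

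For the third row, P = 0.286 + 100 × 0.714 × 0.5 = 36.0 and F = 28.6 + 35.7 = 64.3.

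**Change from visit 1 to visit 9** (negative means improvement):

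- 10 h missed to none, Q5 = 5 at both visits: P gives 50 − 36.0 = +14.0; F gives 50 − 64.3 = −14.3.
- Absent all week to full attendance with Q5 = 3: P gives 30 − 1 = +29; F gives 30 − 100 = −70.
- 7 h missed with Q5 = 5 to none with Q5 = 4: P gives 40 − 40.2 = −0.2; F gives 40 − 60 = −20. The sign is right but the gain almost vanishes.
- No time missed at either visit, Q5 from 6 to 3: −30 on both.

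More generally, take a patient who goes from partial absence a to none with Q5 unchanged, and write q = Q5/10. The change is a × (100q − 1) as printed and −100a × (1 − q) when scaled. For any Q5 from 1 to 9 the first is positive and the second negative.

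**Skips under 6.3.6, read literally.** The questionnaire has six items.

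- Not employed: items 2 to 5 are blank, 4/6 = 66.7%, above 25%. The patient leaves all WPAI analyses, although activity impairment needs only Q6, which was answered.
- Q4 = 0: item 5 is blank, 1/6 = 16.7%, below 25%. Q5 becomes 0, its optimal value, and impairment while working becomes 0 × 10 = 0% for someone who did not work.
- Q2 = Q4 = 0 (for example a week of holiday): a = 0/0, and no rule is given.

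**The case against.** The strongest point is the state of the text. This one formula already shows a lost minus sign and garbled item numbers, and other equations in the SAP were damaged in extraction. An outer bracket could have been lost too. That is unlikely, because the captured brackets balance and the factor of 100 stands outside them, but the source PDF should be checked before the formula is called wrong.

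On the skips, the SAP never says that an item skipped by design counts as missing. It prints both skips, and its item 4 rule makes sense only for employed patients, so the authors may have had only items due in mind. A reader might infer that the plan deliberately treats skips as missing data; the text does not support that. What it shows is a missing exception, which literal programming would turn into exclusions and imputed zeros.

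The Q4 = 0 imputation is also narrow. When Q2 > 0, a = 1 and Q5 has zero weight, so overall impairment is unaffected; only impairment while working is distorted.

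Finally, section 6.2 makes all efficacy analyses beyond the primary one exploratory and rests no claims on them. That limits the consequences but does not make the derivation right.

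**Conclusion.** The point stands within limits. As printed, overall work impairment is understated by exactly 99 × Q2/(Q2+Q4) points in every patient with Q2 > 0, and an individual's improvement can be recorded as deterioration. This assumes that the bracket in the PDF stands where the extracted text puts it. Patients with no health-related absence are unaffected.

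A reader might infer that the work productivity results as a whole are wrong, or that the treatment comparison would reverse. The SAP does not support either. The other three formulas are correctly scaled, and a return to work still shows as improvement on work time missed, which is analysed separately. The reversals shown are for individual patients; a reversal between arms would depend on how absenteeism changes in each arm, and the SAP gives no such data. The primary analysis and the sample size are not touched.

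The skip problem does not depend on the bracket. It rests on a literal reading of 6.3.6 and affects non-employed patients (loss of the activity outcome) and patients with zero hours worked (a best-possible score for impairment while working).

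**What to change.** 1. Check the bracket in section 11.8 against the source PDF. If it stands as extracted, write: overall work impairment = 100 × {Q2/(Q2+Q4) + [1 − Q2/(Q2+Q4)] × Q5/10}.
2. In 6.3.6, state that items skipped by design are not applicable rather than missing, and apply the missing-item rule per outcome: Q6 alone for activity impairment in all patients, and the three work outcomes in employed patients only.
3. When Q4 = 0, do not impute Q5. Impairment while working is not applicable. Overall impairment is 100% if Q2 > 0, because the Q5 term has zero weight; say so explicitly, so that a blank Q5 does not make the result missing in the program.
4. When Q2+Q4 = 0, declare work time missed and overall impairment not computable.

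The cost is one bracket and a few sentences of SAP wording, plus the matching change to the derivation program. No new data are needed.
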